**5.5.1.4. Baseline and Post-Baseline Definition**

Table CGAN. 5.4 describes the rules for determining the patient population and baseline and post-baseline observations for each study phase and type of analysis. When “last of Visit x-x” is used in the table, the last nonmissing observation obtained in the visit interval will be used.

Table CGAN. 5.4 Patient Population with Baseline and Post-Baseline Definitions by Study Period and Type of Analysis

Study Period / Analysis	Patient Population	Baseline Observation	Post-baseline Observation(s)
Study Period III			
Primary / Secondary / Exploratory efficacy analyses (Repeated Measures)	ITT Population with a baseline and at least one post-baseline observation	Visit 3	All Visits 3.01–12
Primary efficacy analyses (Repeated Measures)	PPS with a baseline and at least one post-baseline observation	Visit 3	All Visits 3.01–12
Primary / Secondary / Exploratory efficacy analyses at LOCF endpoint or for average of observed monthly values	ITT Population with a baseline and at least one post-baseline observation	Visit 3	Visit 3.01-12
Quality of Life analyses (Repeated Measures)	ITT Population with a baseline and at least one post-baseline observation	Visit 3	All Visits 3.01–12
Quality of Life analyses at LOCF endpoint or for average of observed monthly values	ITT Population with a baseline and at least one post-baseline observation	Visit 3	Visit 3.01-12
TEAEs	Safety Population	All Visits 1–3. Pre-existing condition that is still ongoing at Visit 1 should be evaluated as baseline values.	All Visits 3.01–12
Serious Adverse Events, Discontinuations due to Adverse Events	Safety Population	NA	All Visits 3.01–12
C-SSRS categorical analyses	Safety population with a baseline and at least one post-baseline C-SSRS assessment	Recent History: All Visits 1–3 excluding lifetime a All Prior History: Visits 1 – 3 including lifetime a	All Visits 3.01–12
Treatment emergent abnormal laboratory values	Safety Population with normal laboratory values at all nonmissing baseline visits (with respect to direction being analyzed) and who have at least one post-baseline observation	All Visits 1–3	All Visits 3.01–12
Treatment emergent immunogenicity	Safety Population, ADA follow-up cohort (See Section 5.5.12.1.6)	Visit 3	All Visits 3.01–12
Treatment emergent changes in vital signs, weight,	Safety Population with a baseline and at least one	Low:	Low:

Study Period / Analysis	Patient Population	Baseline Observation	Post-baseline Observation(s)
and ECGs	post-baseline observation	Minimum value from Visits 1–3  High: Maximum value from Visits 1–3	Minimum value from Visits 3.01–12  High: Maximum value from Visits 3.01–12
Continuous safety analyses (Repeated Measures)	Safety Population with a baseline and at least one post-baseline observation	Last of Visits 1–3	Scheduled visits: 3 < Visits <= 12
Continuous safety analyses – change from baseline to LOCF endpoint (ANCOVA)	Safety Population with a baseline and at least one post-baseline observation	Last of Visits 1–3	Last scheduled visit: 3 < Visit <= 12
Study Period III and IV combined			
Primary / Key Secondary efficacy analyses	ITT Population with a baseline and at least one post-baseline observation	Visit 3	All Visits 3.01–14
Quality of Life analyses	ITT Population with a baseline and at least one post-baseline observation	Visit 3	All Visits 3.01–14
Continuous safety analyses (Repeated Measures)	Safety Population with a baseline and at least one post-baseline observation	Last of Visits 1–3	All Visits 3.01–14
Treatment emergent immunogenicity	Safety Population, ADA follow-up cohort (See Section 5.5.12.1.6)	Visit 3	All Visits 3.01–14
Study Period IV			
Continuous safety analyses – change from baseline to LOCF endpoint (ANCOVA)	Post-treatment Population with a baseline and at least one post-baseline observation	Last of Visits 1–12	Last Visit: 12.01–14
FEAEs	Post-treatment Population	All Visits 1–12. Pre-existing condition that is still ongoing at Visit 1 should be evaluated as baseline values.	All Visits 12.01–14
Serious Adverse Events, Discontinuations due to Adverse Events	Post-treatment Population	NA	All Visits 12.01–14
Follow-up emergent abnormal laboratory values	Post-treatment Population with normal laboratory values at all nonmissing baseline visits (with	All Visits 1–12	All Visits 12.01–14

Study Period / Analysis	Patient Population	Baseline Observation	Post-baseline Observation(s)
	respect to direction being analyzed) and who have at least one post-baseline observation		
Follow-up emergent changes in vital signs, weight and ECGs	Post-treatment Population with a baseline and at least one post-baseline observation	Low: Minimum value from Visits 1–12  High: Maximum value from Visits 1–12	Low: Minimum value from Visits 12.01–14  High: Maximum value from Visits 12.01–14
C-SSRS categorical analyses	Post-treatment Population with a baseline and at least one post-baseline C-SSRS assessment	Recent History: All Visits 1–12 excluding lifetime a All Prior History: Visits 1 – 12 including lifetime a	All Visits 12.01–14

Abbreviations: ADA = Anti-Drug Antibody; ANCOVA = analysis of covariance; C-SSRS = Columbia Suicide Severity Rating Scale; FEAE = follow-up emergent adverse event; ITT = intent-to-treat; LOCF = last observation carried forward; PPS = per protocol set; TEAE = treatment emergent adverse event.  
Note: Visit 3.01 indicates the first unscheduled visit occurring after Visit 3 and prior to Visit 4. Visit 12.01 indicates the first unscheduled visit occurring after Visit 12 and prior to Visit 13. For efficacy and quality of life measures without unscheduled visits data point, Visit 3.01 indicates scheduled collection visits after visit 3.

a Lifetime is captured in the C-SSRS visit 1 CRF.

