- ^d Physical examinations at screening must include a neurological exam.
- ^e Electrocardiograms as single, 12-lead digital will be performed at Visit 1, Visit 3, Visit 12, and Visit 14 or ET. Note: The Visit 3 ECG should be collected prior to blood draws and dosing. Patients must be supine for approximately 5 to 10 minutes before ECG collection, and remain supine, but awake, during ECG collection. For screening only, ECG results will be read locally.
- ^f Vital signs will include body temperature, blood pressure, and pulse. Blood pressure and pulse will be measured in triplicate, in the sitting position, and should be measured prior to blood draws. Blood pressure will be assessed by utilizing a calibrated machine.

- ^e Patient enter into the ePRO diary the occurrence of headaches, headache duration, headache features, severity of headache, and use of headache medication
- ^h In the event of a positive urine leukocyte esterase result, a repeat urine sample will be collected at the next visit and shipped to the central laboratory.
- ⁱ A positive urine test must be followed by a serum pregnancy test for confirmation.
- ^j Biomarker storage samples, immunogenicity, CCI ██████████ PK sampling, and whole blood RNA/epigenetic sample to be performed at the indicated visits and prior to dose administration if the visit is a dosing visit. Samples will be taken in the event of ET. Immunogenicity and PK samples also may be collected in the event of a systemic allergic/hypersensitivity reaction (see Section 9.4.3). The timing of samples will be recorded.
- ^k Patients will receive injections of placebo or galcanezumab after all other visit procedures are completed. Following the first dose at Visit 3, patients will be observed for at least 30 minutes at the site. Following subsequent doses, patients will be observed for at least 30 minutes post-injection if they have a significant adverse event after the first injection and/or they are judged by the investigator to have risk of a significant adverse event after injection.
- ^l The C-SSRS and SHSF (and SHSU, when applicable) will be completed at scheduled and unscheduled office visits.
- ^m Urine pregnancy and biomarker storage sample are collected only for patients rolling over to Study CGAP.

3. Introduction

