To avoid biased reporting, patients must not be told the number of migraine headache days on which study qualification is based.

Study Period III: At the start of the 6-month, double-blind treatment phase (Visit 3), patients meeting all eligibility requirements will be randomized to 1 of 3 treatment groups in a 2:1:1 ratio to receive placebo, 120 mg/month galcanezumab, or 240 mg/month galcanezumab, respectively.

Patients randomized to the 120 mg dose of galcanezumab will receive an initial loading dose of 240 mg (2 injections of 120 mg each at Visit 3 only). To preserve blinding throughout the study, patients in all treatment groups will receive 2 injections of investigational product at each dosing visit. At Visit 3, if available and where local regulations in Japan and ethical review boards/institutional review boards (ERBs/IRBs) allow, patients will also watch a training video designed to address patient expectations with regard to participation in a placebo-controlled trial, and the difference between medical treatment and research.

The patient will be considered enrolled in the study when randomization occurs. During this phase, study procedures at dosing visits must always occur prior to the patient receiving his/her assigned treatment of study drug.

Patients will be given injections of study drug during office visits ([Figure CGAN.5.1](#)). For all treatment groups, subcutaneous injections will be administered once monthly at the dosing visits. At Visit 3 (first dose), patients will be required to remain at the site for observation for at least 30 minutes post-injection. Following subsequent doses, patients will be observed for at least 30 minutes post-injection if they have a significant adverse event after the first injection and/or they are judged by the investigator to have risk of a significant adverse event after injection. Patients will continue to log in and complete the ePRO diary each day. Patients may continue to take their allowed acute migraine headache medication (with some limitations; see concomitant medication study tool) during the treatment phase.

Patients who do not participate in the CGAP study and who complete Study Period III, or who discontinue for any reason during Study Period III, will be expected to enter post-treatment follow-up (Study Period IV).

Patients who discontinue for any reason during Study Period III will be expected to take the measurement for Early Termination (ET).

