##### **5.5.12.1.1. Adverse Events**

Treatment-emergent adverse events are defined as the reported AEs that first occurred or worsened during the post-baseline phase compared with the baseline phase. Pre-existing condition that is still ongoing at Visit 1 should be evaluated as baseline values. For each TEAE, the severity level of the event (mild, moderate, or severe) will be determined by patient or physician opinion. The MedDRA Lowest Level Term (LLT) will be used in the treatment emergent computation. For each LLT, the maximum severity at baseline will be used as the baseline severity. If the maximum severity during post-baseline is greater than the maximum baseline severity, the event is considered to be treatment emergent for the specific post-baseline period. For each patient and TEAE, the maximum severity for the MedDRA level being displayed (PT, High Level Term, or SOC) is the maximum post-baseline severity observed from all associated LLTs mapping to that MedDRA level.

Follow-up emergent adverse events (post-treatment emergent adverse events) are defined similarly. It is an event that first occurred or worsened during the follow-up period (Study Period IV) when compared to the baseline (SP I, SP II, and SP III). Pre-existing condition that is still ongoing at Visit 1 should be evaluated as baseline values.

For events that are gender-specific, the denominator and computation of the percentage will include only patients from the specific gender.

Following summary will be created:

- Overview of AE (SP III)
- TEAEs (SP III)
  - By PT by decreasing frequency
  - By PT by decreasing frequency with an incidence in either galcanezumab treatment group  $\geq 1.5\%$  and greater than placebo.
  - By SOC/PT
  - By maximum severity/PT
- FEAEs (SP IV)
  - By PT by decreasing frequency
  - By SOC/PT
  - By maximum severity/PT
- TEAEs by considered to be related to investigational product by investigator (SP III)
- Treatment Emergent Adverse Events that started on Treatment phase and Continuing in Post-Treatment Phase (SP III, SP IV combined)
- SAEs (SP III, SP IV separately)
- AEs leading to discontinuation (SP III, SP IV separately)

Listing of Subjects with TEAE or FEAE (SP III, SP IV combined) will be created.

Listing of Adverse Events Leading to Discontinuation and Serious Adverse Events (SP I, SP II, SP III, SP IV combined) will be created.

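### The SAP's TEAE baseline takes in all of Visit 3 with no cut at the first injection, so reactions seen on site after that dose may not count as treatment-emergent

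*SAP*

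**What the plan says.** In SAP Section 5.5.1.4, Table CGAN. 5.4, the Study Period III row for TEAEs gives the baseline as "All Visits 1–3. Pre-existing condition that is still ongoing at Visit 1 should be evaluated as baseline values" and the post-baseline window as "All Visits 3.01–12". The note under the table explains that "Visit 3.01 indicates the first unscheduled visit occurring after Visit 3 and prior to Visit 4". SAP Section 5.5.12 applies this table to all safety measures unless stated otherwise, so the hypersensitivity and injection-site TEAE analyses inherit it.

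SAP Section 5.5.12.1.1 sets the treatment-emergence rule at LLT level: "For each LLT, the maximum severity at baseline will be used as the baseline severity". It continues: "If the maximum severity during post-baseline is greater than the maximum baseline severity, the event is considered to be treatment emergent".

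The first dose falls inside Visit 3. Protocol Section 5.1 says: "At Visit 3 (first dose), patients will be required to remain at the site for observation for at least 30 minutes post-injection".

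The serious adverse event and adverse-event discontinuation rows of the same table have no baseline (NA), but their Study Period III window also starts at Visit 3.01.

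**The concern.** The boundary between baseline and post-baseline is defined by visit, while the event that should define it, the first injection, happens in the middle of a visit. Injection-site and hypersensitivity reactions to a first dose are likely to appear in the minutes afterwards. Visit 3 is also the only dosing visit at which every patient must be observed; after later doses, observation is conditional.

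Taken literally, the table has two effects on a reaction seen in that window. The reaction itself is not counted as a TEAE. It also sets the baseline severity for its LLT, so a later reaction of equal or lower severity is not counted either. Follow-up-emergent events do not recover it, because their baseline runs from Visit 1 to Visit 12. The TEAE flag also feeds the non-serious category of the registry summary (SAP Section 5.9).

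At stake are the absolute TEAE incidence and the between-arm difference for injection-related events. There is also a risk that two programmers working from different sections of the SAP would produce different counts.

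**Working it through.** The plan states no figure to reproduce on this point. The check applies the rule to cases and then shows scale under an assumption.

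**1. Does anything cut the adverse event baseline at the injection?** The SAP sets a dosing or same-day boundary for several other data types:
- Baseline body weight is the last value before the Visit 3 injection (Section 5.5.4, Table CGAN. 5.8).
- Concomitant medication has same-day injection rules (Section 5.5.9).
- Questionnaires have an injection-day rule (Section 5.5.1).
- Visit 3 diary data go to Month 1 (Section 5.4.1).
- The baseline for improvement in suicidal ideation is the measurement just before treatment (Section 5.5.12.1.2).

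The TEAE row has no such boundary, and neither document says which visit is assigned to an event that starts after the Visit 3 injection.

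**2. The rule applied to cases.** Within one LLT, code none = 0, mild = 1, moderate = 2. The event is treatment-emergent if maximum post-baseline severity exceeds maximum baseline severity.

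| After Visit 3 injection | Later | Visit 3 all baseline | Cut at first injection |
|---|---|---|---|
| Mild | None | 0 > 1: no | 1 > 0: yes |
| Mild | Mild | 1 > 1: no | 1 > 0: yes |
| Moderate | Mild | 1 > 2: no | 2 > 0: yes |
| Mild | Moderate | 2 > 1: yes | 2 > 0: yes |
| None | Mild | 1 > 0: yes | 1 > 0: yes |

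The two readings differ in the first three rows. They agree when a later event is worse or when there was no reaction at Visit 3.

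**3. Serious events and discontinuations.** With no baseline comparison, severity masking does not arise. The window still begins at Visit 3.01, so an event labelled Visit 3 would fall outside the Study Period III summary. It would still appear in the listing of serious events and discontinuations across Study Periods I to IV (Section 5.5.12.1.1).

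**4. Illustration of scale.** Inputs: injection-site pain of 17% on galcanezumab and 6% on placebo in the proof-of-concept study (protocol Section 3.2). Assume a share f of affected patients drops out of the TEAE count, equal in both arms. The documents do not give f. Counted rates are 17% × (1 − f) and 6% × (1 − f).

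| f | Galcanezumab | Placebo | Difference (points) |
|---|---|---|---|
| 0 | 17.0% | 6.0% | 11.0 |
| 10% | 15.3% | 5.4% | 9.9 |
| 25% | 12.75% | 4.5% | 8.25 |
| 50% | 8.5% | 3.0% | 5.5 |

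The ratio stays at 17/6 = 2.83 throughout, because f is assumed equal in both arms. That study dosed every 14 days for six doses, so neither the rates nor any plausible f carry over directly to monthly dosing.

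**The case against.** The strongest reply is that a pre-dose baseline is plainly intended and no data would be lost. Footnote k of the protocol's Schedule of Activities says: "Patients will receive injections of placebo or galcanezumab after all other visit procedures are completed". Adverse event review is a listed Visit 3 activity, so the scheduled review comes before dosing. Protocol Appendix 1 defines a TEAE as absent before treatment. The SAP's timing tables include hypersensitivity TEAEs during and within 30 minutes of administration (Section 5.5.12.1.1.1), and injection-site TEAEs during and within 60 minutes (Section 5.5.12.1.1.2). Neither excludes the first dose. If programming already separates events by injection time, f = 0.

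Most of this stands as evidence of intent. It does not settle the rule. The order of procedures fixes when scheduled assessments such as ECGs and vital signs are taken. An adverse event is recorded when it occurs, and the observation period exists to catch events after the procedures are finished. The definition and the timing tables show what the baseline row ought to deliver, but the row does not say it.

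A second objection also stands in part. Dose time is recorded for every administration (protocol Section 7.2.1), but the documents do not show that onset clock time is collected for every adverse event. The SAP allows that the timing categories for hypersensitivity and injection-site events may be missing. A cut at the injection therefore needs a default rule for unknown times.

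**Conclusion.** The point holds as a defect in the written rule. Table CGAN. 5.4 puts the whole of Visit 3 in the TEAE baseline, although the first injection and its observation period fall within that visit. If post-injection events are assigned to Visit 3, the first-dose reaction is not a TEAE, and later events of the same LLT with equal or lower severity are masked. Worse events still count. Serious events and discontinuations escape the masking but share the late window start.

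A reader might infer that the trial's TEAE tables do omit first-dose reactions, or that the difference between arms is understated by a known amount. The documents support neither. The visit assignment is unstated, several sections point to a pre-dose baseline, and the size depends on an assumed share whose range includes zero. The 17% and 6% calculation shows only how the effect would scale.

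The text should still be corrected, because the operative table conflicts with the protocol's own TEAE definition, the events concerned are first-dose reactions, and the correction is small.

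**What to change.** In Table CGAN. 5.4, state that adverse events starting or worsening at or after the first injection on the Visit 3 date are post-baseline, and that earlier events are baseline. Apply this to the Study Period III TEAE, serious adverse event and adverse-event discontinuation rows, and to the Study Period III hypersensitivity and injection-site analyses.

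Derive the cut from the recorded dose time and, where collected, the eCRF event-timing categories. For events dated on the Visit 3 day with unknown onset time, count them as post-baseline unless the record shows they were present before dosing.

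The cost is a few lines of SAP text and one derivation; if programming already uses the injection time, only the text changes. The downside is that a few pre-dose same-day events of unknown time may be counted as TEAEs. The proviso about records of pre-dose presence limits this.

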### **5.5.2. Patient Disposition**

The number of ITT patients who complete the study or discontinue early will be tabulated for all treatment groups for Study Period III and Study Period IV separately, both overall and by visit. Reasons for discontinuation will be compared between treatment groups using Fisher's exact test for study period III with the ITT population. Descriptive statistics only will be presented for the treatment groups in Study Period IV with post-treatment population. Subcategories of discontinuation due to subject decision will be summarized too.

Listing of Subjects who discontinued for SP III or SP IV will be created for ITT population.

Patient allocation by investigator site will be summarized (the number of screened, randomized, discontinued from SP III, entered for SP IV, discontinued from SP IV, entered CGAP study) for all patients.

Summary of Reasons for Screen Failure will be created for all screen failure patients.

Listing of Detailed Reasons for Screen Failure will be created for all screen failure patients.

Listing of Patient population (e.g. PPS, safety population) by treatment will be created for all study periods for ITT population.

### **5.5.3. Important Protocol Deviations**

Listings of subjects with important protocol deviations will be provided for ITT population. The following list of important protocol deviations will be determined before DBL. Detail criteria and methods will be specified in a separate document which also specify exclusion of PPS/ITT/safety population:

- Violation of informed consent : (e.g. Lack of informed consent or late informed consent)
- Serious Adverse event not reported
- Deviation related to inclusion/exclusion criteria
- Deviation of the rescreen criteria
- Deviation of the operation of Visit
- Deviation of the discontinuation criteria
- Deviation of study treatment dosing
- Deviation of concomitant drug and therapy
- Other important protocol deviations as determined by the Lilly clinical/medical group

Summary of important protocol deviations will be created for each arm and overall. The summary will be made for

- Baseline and SP III
- SP IV

Listing of Important Protocol Deviations (include flags whether affected to PPS/ITT/safety or not) will be made for

- Baseline and SP III
- SP IV

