#### 5.5.1.3. Analysis Populations

Analysis populations are defined below:

**All Patients:** All patients who signs informed consent.

**All Randomized Patients (ARP):** All patients who are randomized at Visit 3.

**Intent-to-Treat (ITT) Population:** All patients who are randomized at Visit 3 and received at least one dose of the study drug. Patients in the ITT population will be analyzed according to the treatment that they were randomized to. Unless otherwise specified, the ITT population will be the primary population on which statistical analysis will be performed.

**Post-treatment Population:** All patients who entered the post-treatment phase (Study Period IV) as indicated by entering any post-treatment visit. Patients in the post-treatment population will be analyzed according to the treatment that they were randomized to at Visit 3. Post-treatment Population is a subset of ARP.

**ADA Follow-up Cohort:** All patients who are post-treatment population and have both baseline and at least one postbaseline ADA assessment during SP IV.

**Per Protocol Set (PPS):** Intent-to-treat population who has no important protocol deviation which impacts efficacy analysis. Details will be specified in Section 5.5.3.

**Safety Population:** This is the same as the ITT population except the assigned arm definition. It is determined by modal treatment the patient received during the double-blind treatment period (up to the injection visits if they discontinue early). For determining modal treatment, do not consider the loading dose visit for patients assigned to an LY120-mg treatment group, but do consider it for patients assigned to the placebo and LY240-mg treatment groups. If there are 2 or more modes, then add the loading dose visit and recalculate the mode. If there is still a tie, the highest dose of the modes is to be used.

**Example 1:** Suppose a patient, randomized as LY120-mg treatment group, discontinues at Visit 5 (Month 1) who has LY 240-mg loading dose at Visit 3 (Month 0) and no dose at Visit 5 (Month 1). It implies mode is not unique, because Visit 3 dosing is omitted. Its mode is 0mg, 120mg, 240mg (counted as zero at each dose). Then the patient is assigned to LY240-mg arm group (the highest dose) as safety population.

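### SAP 5.5.3 allows deviation-based exclusion from the ITT and safety populations, contradicting the definitions in SAP 5.5.1.3 and Protocol 10.2

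*SAP*

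**What the plan says.** SAP 5.5.3 lists nine categories of important protocol deviation. Some concern entry to the trial: consent, eligibility and rescreening. Others can arise after randomisation: visit conduct, discontinuation criteria, dosing, concomitant treatment and unreported serious adverse events. The last is open: "Other important protocol deviations as determined by the Lilly clinical/medical group". On timing, the section says "The following list of important protocol deviations will be determined before DBL". On consequences, it says "Detail criteria and methods will be specified in a separate document which also specify exclusion of PPS/ITT/safety population". A planned output carries the same idea: "Listing of Important Protocol Deviations (include flags whether affected to PPS/ITT/safety or not) will be made for" two periods, baseline with Study Period III, and Study Period IV.

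The population definitions are in SAP 5.5.1.3:

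- ITT: "All patients who are randomized at Visit 3 and received at least one dose of the study drug", analysed as randomised.
- Safety: "This is the same as the ITT population except the assigned arm definition".
- PPS: "Intent-to-treat population who has no important protocol deviation which impacts efficacy analysis", with details referred to 5.5.3.

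Protocol 10.2 gives the same ITT and PPS definitions. The ITT entry in Protocol Appendix 1 says that patients are analysed in their allocated group whatever their adherence to treatment. Protocol 10.3.3.1 places the primary analysis on ITT. SAP 5.5 states that the SAP takes precedence over the protocol's statistical plan.

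**The concern.** The definitions admit every randomised and dosed patient to ITT and safety without exception. Section 5.5.3 then hands exclusion from those same populations to a document that is not part of the plan. A reader of the protocol and SAP cannot tell who will be in the primary analysis.

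The stake is the randomised comparison. A deviation that occurs after randomisation can depend on how the patient is doing. For example, Protocol 8.2 requires a patient who needs another effective preventive in Study Period III to leave the study before starting it. A breach of that rule may therefore reflect poor response. If such patients could be taken out of ITT, the arms would be compared after selection on something related to outcome.

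The planned robustness check would also suffer. SAP 5.5.10.2 repeats the primary analysis on the PPS in place of ITT, and that contrast is informative only if ITT itself is untouched by deviations.

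**Working it through.** No planned figure is in dispute, so the check is a comparison of texts.

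**Step 1: what each population rests on.**

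| Population | Definition (SAP 5.5.1.3) | Do deviations enter the definition? | Named in the 5.5.3 exclusion sentence? |
|---|---|---|---|
| ITT | Randomised at Visit 3 and at least one dose | No | Yes |
| Safety | Same patients as ITT, arm set by modal treatment received | No | Yes |
| PPS | ITT patients without an important deviation affecting efficacy | Yes, with a pointer to 5.5.3 | Yes |

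For the PPS the two sections agree. For ITT and safety they do not. Only the PPS definition refers the reader to 5.5.3.

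**Step 2: is it a single slip?** The three populations are named together twice in 5.5.3, once in the exclusion sentence and once in the flags of a planned listing ("include flags whether affected to PPS/ITT/safety or not"). The first uses the word exclusion and the second speaks only of being affected. The contradiction rests on the first. The second shows that the same grouping was carried into an output.

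**Step 3: does it reach the primary analysis?** Yes. Protocol 10.3.3.1 and SAP 5.5.1 place efficacy analysis on ITT. Deviation-based exclusion has a stated home in SAP 5.5.10.2, as the PPS sensitivity analysis. Nothing there or in 5.5.1.3 extends it to ITT.

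**Step 4: when are the decisions made?** Section 5.5.3 says before database lock without saying which lock. SAP 5.8.1 reports Study Period III deviations at the interim analysis, and SAP 5.7 unblinds the analysis team only after the interim lock. For Study Period III the natural reading is therefore a blinded decision before the interim lock.

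**Step 5: can a size be given?** Suppose a fraction *p* of one arm is removed and those patients differ on average by *d* from the patients kept. The arm mean before removal is (1 − *p*)·*m* + *p*·(*m* + *d*) = *m* + *p*·*d*, where *m* is the mean of those kept. Removal therefore shifts the arm mean by −*p*·*d*, and the treatment contrast moves by that amount unless the other arm shifts equally. The documents give neither *p* nor *d*, nor the criteria that would determine them. The formula shows the mechanism, but no number follows. Blinding does not set *d* to zero when the deviation itself is related to outcome.

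**The case against.** The strongest reply is that 5.5.3 is loosely worded and the operative definitions are clear. Several points support this:

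- Section 5.5.3 opens by planning deviation listings for the ITT population, so patients with deviations are expected to be in it.
- SAP 5.5.10.2 ties exclusion to the PPS.
- A dosing record can decide ITT membership under the definition itself, since one dose is required. A dosing error can change a patient's safety arm through the modal-treatment rule without removing anyone. A flag for being affected may mean no more than that.
- The separate document may list no ITT exclusions, or only consent failures.
- The list is fixed before lock, which guards against choices made with knowledge of treatment.

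Most of this stands. The flags alone would be weak evidence, and the timing deserves credit. But none of it explains the word exclusion applied to ITT and safety. If the separate document excludes nobody from those populations, the sentence should say so.

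The timing protection also has limits. It is inferred rather than stated, and it is clearest for Study Period III. The flagged listing also covers Study Period IV. By the final lock the sponsor's medical staff are among those unblinded (SAP Table CGAN.5.10), and the combined Study Period III and IV analyses on ITT and safety are produced then (SAP 5.8.1).

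It is also true that ITT already omits undosed patients. That is a stated rule, and it does not license further unstated ones.

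**Conclusion.** The contradiction is real, is in current text, and concerns the primary analysis population. It should be corrected. What is established is a permission: as written, the SAP allows deviation-based exclusions from ITT and safety under criteria that cannot be seen. The size of any effect cannot be derived.

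A reader might infer more, and the documents do not support it:

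- **That patients will be removed from ITT for dosing, concomitant treatment or discontinuation deviations.** Section 5.5.3 links no category to ITT or safety and does not say that any removal will occur.
- **That the primary analysis becomes a per-protocol analysis.** This would need the PPS criteria to be applied to ITT, and nothing says so.
- **That safety events will be hidden.** A deviation listing with population flags is planned. So is a listing of serious adverse events and discontinuations due to adverse events across all study periods (SAP 5.5.12.1.1), although its population is not stated.
- **That the trial loses a definite amount of power.** No exclusion rate is given, and loss from random exclusion would not measure the bias at issue.

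The conclusion rests on reading exclusion in its ordinary sense and on the separate document being outside the material available.

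**What to change.** In SAP 5.5.3, limit deviation-based exclusion to the PPS by deleting ITT and safety from the exclusion sentence. Reword the listing flags to show PPS status only. If a note on modal-treatment arm assignment is wanted, make it a separate flag worded as such. State that no protocol deviation removes a randomised and dosed patient from ITT or safety.

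If an exception is unavoidable, for example no valid informed consent, name it in SAP 5.5.1.3 as the only one. State that it is decided before the interim database lock while the team is blinded. Align the separate deviation document with this wording.

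The cost is a short SAP edit and a consistency check of one supporting document. No sample size, model, endpoint or other planned figure changes.
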